7.2. Follow-up

7.2.1. Visit 2, Day 9, Clinic Visit (8 days [+2 days] post first study vaccination)

- Study personnel will review the Memory Aid information with subjects and assess and record all AE/SAEs and concomitant medications on the appropriate data collection form.
- Counsel women of childbearing potential on contraception and avoidance of pregnancy.
- If indicated by review of Memory Aid, obtain vital signs.
- A targeted physical examination may be performed by a study clinician licensed to make medical diagnoses and listed on the Form FDA 1572 as the site PI or sub-I, if indicated based on review of interim medical history.
- Examine the vaccination site for Dose 1.
- Approximately 10 mL of venous blood will be collected for safety labs.

7.2.2. Visit 3, Day 15, Clinic Visit (14 days [+2 days] post first study vaccination)

- Study personnel will review interim medical history with subjects and assess and record all AE/SAEs and concomitant medications on the appropriate data collection form.
- Counsel women of childbearing potential on contraception and avoidance of pregnancy.
- If indicated, obtain vital signs.
- A targeted physical examination may be performed by a study clinician licensed to make medical diagnoses and listed on the Form FDA 1572 as the site PI or sub-I, if indicated based on review of interim medical history.
- Approximately 40 mL of venous blood will be collected for isolation of PBMCs.

7.2.3. Visit 4, Day 22, Dose 2, Clinic Visit (21 days [+2 days] post first study vaccination)

- Eligibility criteria will be reviewed with subjects prior to the second study vaccination to assure continued eligibility.
- Obtain interim medical history by interview of subjects prior to the second study vaccination and note any changes since the previous visit.
- All concomitant medications will be recorded on the appropriate data collection form prior to the second study vaccination.
- All AE/SAEs will be assessed and recorded on the appropriate data collection form prior to the second study vaccination.
- Vital signs, including oral temperature, pulse, and blood pressure, will be obtained prior to the second study vaccination. Subjects must not eat or drink anything hot or cold, or smoke within 10 minutes prior to taking oral temperature.

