- A targeted physical examination may be performed prior to the second study vaccination by a study clinician licensed to make medical diagnoses and listed on the Form FDA 1572 as the site PI or sub-I, if indicated based on review of interim medical history.
- Counsel women of childbearing potential on contraception and avoidance of pregnancy.
- A urine or serum pregnancy test will be performed within 24 hours prior to the second study vaccination on all female subjects of childbearing potential. Results must be negative and known prior to the second study vaccination.

- Approximately 10 mL of venous blood will be collected prior to the study vaccination for antibody assays.
- Pre-administration reactogenicity assessments will be performed prior to the second study vaccination to establish baseline. Subjects will then receive a single dose of study vaccine via IM injection into the deltoid muscle of the same arm that received Dose 1 as long as there is no interference with the reactogenicity assessment. The site of injection (right or left arm) and time of administration will be recorded on the appropriate data collection form. Subjects will be observed in the clinic for at least 20 minutes after the second study vaccination. The study vaccination site for Dose 2 will be examined, and any AE/SAEs will be assessed and recorded on the appropriate data collection form prior to discharge from the clinic.
- Subjects will be provided with a Memory Aid and other study-related materials to record daily oral temperature, solicited injection site and systemic reactions, any unsolicited AEs, and concomitant medications. Subjects will be encouraged to take their temperature around the same time each day. Subjects will be instructed on how to use the Memory Aid and how to measure and record AEs prior to discharge from the clinic. Subjects will be instructed to notify the study center if they develop any severe reactions after the second study vaccination. If the site PI or appropriate sub-I deems the reaction severe enough, s/he will give further instructions on the proper course of action, including a return to the clinic for immediate evaluation if appropriate.

7.2.4. Visit 5, Day 30, Clinic Visit (8 days [+2 days] post second study vaccination)

- Study personnel will review the Memory Aid information with subjects and assess and record all AEs/SAEs and concomitant medications on the appropriate data collection form.

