7.4. Early Termination Visit

The following activities will be performed at the early termination visit for subjects who withdraw, or are withdrawn or terminated from the study:

- Obtain interim medical history by interview of subjects and note any changes since the previous visit.
- Memory Aid information will be reviewed with subjects (if within 8 days after a M-001 study vaccination).
- If indicated by medical history, obtain vital signs. Subjects must not eat or drink anything hot or cold, or smoke within 10 minutes prior to taking oral temperature.
- Review and record all concomitant medications (if prior to 21 days after the last study vaccination).
- Information regarding AEs/SAEs will be recorded on the appropriate data collection form. AEs will be limited to SAEs if after 21 days following the second M-001 study vaccination.
- A targeted physical examination may be performed by a study clinician licensed to make medical diagnoses and listed on the Form FDA 1572 as the site PI or sub-I, if indicated based on review of interim medical history.
- Examine study vaccination site, and perform post-administration reactogenicity assessment (if within 8 days after a M-001 study vaccination).
- Approximately 10 mL of venous blood will be collected for clinical labs, and performed by the central (clinical) laboratory (if within 7 (+2) days after a M-001 study vaccination), or if indicated based on review of interim medical history, or to follow-up on any grade 2 or higher laboratory abnormalities.
- Approximately 10 mL of venous blood will be collected for influenza antibody assays.
- Approximately 40 mL of venous blood will be collected for isolation of PBMCs.

7.5. **Unscheduled Visit**

Unscheduled visits may occur at any time during the study. Any of the following activities may be performed:

- Review Memory Aid (if within 8 days after the previous study vaccination, inclusive of vaccination day).
- Review and record all concomitant medications (if prior to 21 days after the last study vaccination).
- Counsel women of childbearing potential on contraception and avoidance of pregnancy.
- All AEs/SAEs will be recorded on the appropriate data collection form. AEs will be limited to SAEs if after 21 days after the last study vaccination.
- Obtain interim medical history by interview of subjects and note any changes since the previous visit (if indicated).

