- If indicated, obtain vital signs. Subjects must not eat or drink anything hot or cold, or smoke within 10 minutes prior to taking oral temperature.
- A targeted physical examination may be performed by a study clinician licensed to make medical diagnoses and listed on the Form FDA 1572 as the site PI or sub-I, if indicated based on review of interim medical history.
- Examine study vaccination site and perform post- administration reactogenicity assessment (if within 8 days after the last study vaccination, inclusive of vaccination day).
- Approximately 10 mL of venous blood will be collected for clinical labs, and performed by the central (clinical) laboratory (if within 9 days after a M-001 study vaccination), or if indicated based on review of interim medical history, or to follow-up on any laboratory abnormalities determined to be AEs.

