8.2.1. Clinical Laboratory Evaluations

Urine or serum pregnancy tests will be performed by the local or site laboratory within 24 hours prior to each study vaccination (Day 1 (Visit 01) and approximately Day 22 (Visit 04), and Day 172 (Visit 09)) on all female subjects of childbearing potential. Results must be negative and known prior to randomization on Day 1 (Visit 01) and administration of each study vaccination to be eligible for participation in the study and receipt of each dose of study vaccine, respectively.

Clinical safety laboratory parameters to be evaluated after receipt of the first two doses of study vaccine will include: WBC, hemoglobin, platelets, ALT, total bilirubin, and creatinine. These evaluations will be performed by the central (clinical) laboratory. Venous blood samples (approximately 10 mL) will be collected from each subject prior to vaccination at baseline (Visit 01) and approximately 8 days after Dose 1 and Dose 2 of study vaccination (Visits 02 and 05, respectively).

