9.5. Halting Rules

Further enrollment and study vaccinations will be halted for DSMB review/recommendation if any of the following are reported:

- Any subject experiences ulceration, abscess, or necrosis at the injection site related to study product administration.
- Any subject experiences laryngospasm, bronchospasm, or anaphylaxis within 1 day after administration of study product that is considered related to study product.
- Two or more subjects experience generalized urticaria within 3 days after administration of study product that is considered related to study product.
- Any subject experiences a study vaccine-related SAE from the time of the first study vaccination through the subject's last study visit.
- Any subject experiences acute weakness of limbs and/or cranial nerve innervated muscles (description of potential signal of GBS) after administration of study product.

This study will also be halted for DSMB review/recommendation if, within 8 days after administration of either of the first 2 vaccine doses of M-001 or placebo, any of the following occurs:

- 5% or more of subjects (with a minimum of 3 subjects) who received at least one dose of study vaccine to date experience the same severe (Grade 3) study vaccine-related injection site reaction. Ecchymosis (bruising), erythema (redness), and induration (hardness)/edema (swelling) will also be measured in mm but size will not be used as halting criteria.
- 5% or more of subjects (with a minimum of 3 subjects) who received at least one dose of study vaccine to date experience the same severe (Grade 3) study vaccine-related subjective systemic reaction, for which the severity (grade) is corroborated by study personnel.
- 5% or more of subjects (with a minimum of 3 subjects) who received at least one dose of study vaccine to date experience the same severe (Grade 3) study vaccine-related quantitative systemic reaction.
- 5% or more of subjects (with a minimum of 3 subjects) who received at least one dose of study vaccine to date experience the same severe (Grade 3) study vaccine-related clinical safety laboratory AE.

Grading scales for solicited injection site and systemic (subjective and quantitative) reactions are included in [Section 9.2.2](#).

If any of the halting rules are met following any subject receipt of any study vaccination, then this study will not continue with the remaining enrollments or study vaccinations without a review by and recommendation from the DSMB to proceed.

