9.6.2. Data and Safety Monitoring Board (DSMB)

Safety oversight will be conducted by a DSMB that is an independent group of experts that monitors subject safety and advises DMID. The DSMB members will be separate and independent of study personnel participating in this trial and should not have scientific, financial or other conflict of interest related to this trial. The DSMB will consist of members with appropriate expertise to contribute to the interpretation of the data from this trial.

The DSMB will review study progress and participant, clinical, safety, and reactogenicity data at the following time points. A review of immunogenicity data will be performed as specified below.

- Data review for safety at study-specific time frames; at least annually.
- After all 8-day post second study vaccination safety data are available for all study participants.
- Final review meeting: 6 to 8 months after clinical database lock to review the cumulative unblinded safety and immunogenicity data for this trial. The data will be provided in a standard summary format. The DSMB may be asked to provide recommendations in response to questions posed by DMID.
- Ad hoc when a halting rule is met, for immediate concerns regarding observations during this trial, or as needed.

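### As worded, the Grade 3 laboratory halting clause reaches only the first of the three permitted safety-draw days, so a compliant result from 9 or 10 days post dose may not count toward the automatic halt

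*Protocol*

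**What the plan says.** Protocol Section 9.5 lists four rules with a threshold of 5% of subjects and a minimum of 3. All four apply to events "within 8 days after administration of either of the first 2 vaccine doses of M-001 or placebo". The fourth concerns laboratory results and counts subjects "who received at least one dose of study vaccine to date experience the same severe (Grade 3) study vaccine-related clinical safety laboratory AE". The time limit carries no tolerance.

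Section 8.2.1 sets the post-dose safety bloods at "approximately 8 days after Dose 1 and Dose 2 of study vaccination (Visits 02 and 05, respectively"). The visit headings in Section 7.2 give the windows: "Visit 2, Day 9, Clinic Visit (8 days [+2 days] post first study vaccination") and "Visit 5, Day 30, Clinic Visit (8 days [+2 days] post second study vaccination"). Appendix A shows the same +2 windows and no other scheduled post-dose safety bloods.

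Other laboratory limits run past day 8. The early termination visit (Section 7.4) takes bloods "if within 7 (+2) days after a M-001 study vaccination", and the unscheduled visit (Section 7.5) "if within 9 days after a M-001 study vaccination". Section 9.6.2 says that the halting rules are monitored through web reports from the Statistical and Data Coordinating Center (SDCC).

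**The concern.** The 8-day limit suits solicited reactions, which are recorded daily through 7 days after each of the first two doses. It suits laboratory events poorly, because an abnormality is normally dated only by its blood draw, and that draw may properly come after day 8. On the literal reading, whether a related Grade 3 value counts toward the study-level halt depends on which permitted day the subject attends. Late-drawn subjects still enlarge the denominator, so the rule becomes harder to meet as more visits use their window.

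At stake is a participant-protection rule that is meant to stop enrollment and dosing without anyone having to exercise judgment. No estimate, test or table in the SAP depends on it.

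**Working it through.** **Day arithmetic (all from the text).** Visit 02 is study Day 9 after a Day 1 dose: 9 − 1 = 8. Visit 05 is study Day 30 after a Day 22 dose: 30 − 22 = 8. This agrees with the offset of 8 days in both visit headings. With +2 and no minus side, the permitted draw days are 8, 9 and 10 post dose. The halting window is days 0 to 8. The overlap is day 8 only: 1 of 3 permitted days after each dose. This counts days, not draws, and day 8 is the target day. The uncovered days are study Days 10–11 after Dose 1 and 31–32 after an on-time Dose 2.

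Section 11.3.1 counts 8 days inclusive of the vaccination day. On that count the window is days 0 to 7 and covers no scheduled draw.

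**Threshold.** At 120 dosed, 0.05 × 120 = 6 subjects. At 60 dosed, 0.05 × 60 = 3.

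**Illustration, single check at full enrollment.** Let p be the rate per draw of the same related Grade 3 laboratory event, pooled over both arms, and s the share of draws made on day 8. With two independent draws, the chance that a subject is counted is q = 1 − (1 − p·s)². The chance of meeting the threshold is P(X ≥ 6), with X binomial (120, q). For p = 3%:

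- s = 1: q = 1 − 0.97² = 0.0591, giving 0.719
- s = 0.75: q = 1 − 0.9775² = 0.0445, giving 0.445
- s = 0.5: q = 1 − 0.985² = 0.0298, giving 0.149

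| p per draw (assumed) | 0% late | 25% late | 50% late |
|---|---|---|---|
| 5% | 0.980 | 0.883 | 0.546 |
| 3% | 0.719 | 0.445 | 0.149 |
| 2% | 0.340 | 0.149 | 0.033 |
| 1% | 0.033 | 0.010 | 0.001 |
| 0.5% | 0.0014 | 0.0003 | <0.0001 |

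**Illustration, rule checked as data accrue.** This used 20,000 simulated trials with 120 subjects entering evenly over 75 days and results at 8 and 29 days after entry. The halt is met when the count is at least 3 and at least 5% of those dosed to date. The chance that it is met before the last Dose 2 is given:

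| p per draw (assumed) | 0% late | 25% late | 50% late |
|---|---|---|---|
| 5% | 0.977 | 0.876 | 0.543 |
| 3% | 0.714 | 0.453 | 0.173 |
| 2% | 0.360 | 0.174 | 0.050 |
| 1% | 0.051 | 0.021 | 0.006 |

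**What the pooled rates imply.** Half the subjects receive saline. If they contribute essentially no related Grade 3 events, the M-001 arm rate is about 2p per draw, and the share of M-001 recipients affected over two draws is 1 − (1 − 2p)². That is 19% at p = 5%, about 12% at 3% and about 8% at 2%. The largest contrasts in the tables therefore belong to a clearly toxic product.

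**The case against.** The strongest reply is that eight days is the protocol's label for the Visit 02 and 05 data. Section 8.2.1 says approximately, and Section 9.6.2 schedules a board review "After all 8-day post second study vaccination safety data are available for all study participants", which makes sense only if draws inside the +2 window are 8-day data. The clause also limits when an event occurs, not when blood is taken. The comparison limits in Sections 7.4 and 7.5 stop at day 9, short of the day 10 visit limit, so they may show loose day-labelling and no deliberate choice. The SDCC report or the board charter may already count nominally, and neither is available here.

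Much of this is fair. The nominal reading is plausible and may be what was intended. But Section 9.5 does not adopt it, and Section 9.1 repeats an 8-day limit for laboratory abnormalities without tolerance. The draw is usually the only dated evidence of when a laboratory event occurred. A programmed report needs a definite last day, and the text supports more than one.

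Safeguards limit the harm. A Grade 2 or 3 value that does not fall to Grade 1 or less blocks that subject's next dose (Sections 5.3 and 5.4.3), and any related serious event halts the study. The sponsor may suspend dosing, and the board may meet ad hoc. None of these restores the automatic count. Dose-blocking protects only the individual, the serious-event halt misses a Grade 3 value that is not serious, and suspension and ad hoc review are discretionary. The board review tied to 8-day post-Dose 2 data comes after all M-001 doses have been given.

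The objection that the probabilities rest on assumptions also stands.

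**Conclusion.** The concern holds. Followed as written, the laboratory clause covers 1 of 3 permitted draw days after each dose and can leave out compliant results from 9 or 10 days post dose while keeping those subjects in the denominator. That much rests on the text alone.

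The practical size is unknown. The event rates, late-draw shares, independence of the two draws and even accrual are all assumptions. Under them the reading matters when the pooled rate is about 2% per draw or higher, which is where the rule is meant to act. At 1% it fires about 3% to 5% of the time even if every draw counts. This should be corrected because it concerns a safety stopping rule and costs almost nothing, but it is a wording defect with partial safeguards and does not affect the trial's analyses.

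**What to change.** In Section 9.5, give the laboratory rule its own time limit: any result from the Visit 02 or Visit 05 safety draw, including the +2 day window, that is, through 10 days after the dose. Leave the 8-day limit for the three reactogenicity rules. Confirm that the SDCC halting report uses the same limit. All 3 of 3 permitted draw days are then covered after each dose.

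Matching wording in Protocol Section 9.1 and SAP Section 4.5.1 would be tidy but is optional, and Section 3.2.1 needs no change. The cost is one line of protocol text and one programming check, with no new visits, samples or data. If the report already counts by visit, the edit simply documents that.

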9.6. Safety Oversight (ISM plus DSMB)

9.6.1. Independent Safety Monitor (ISM)

The ISM is a physician with relevant expertise whose primary responsibility is to provide independent safety monitoring in a timely fashion. The ISM will review SAEs and other AEs as needed and provide an independent assessment to DMID. Each participating study site will have an ISM with experience in infectious diseases or internal medicine, in close proximity to the participating VTEU site, and have the authority to readily access study participant records.

9.6.2. Data and Safety Monitoring Board (DSMB)

Safety oversight will be conducted by a DSMB that is an independent group of experts that monitors subject safety and advises DMID. The DSMB members will be separate and independent of study personnel participating in this trial and should not have scientific, financial or other conflict of interest related to this trial. The DSMB will consist of members with appropriate expertise to contribute to the interpretation of the data from this trial.

The DSMB will review study progress and participant, clinical, safety, and reactogenicity data at the following time points. A review of immunogenicity data will be performed as specified below.

- Data review for safety at study-specific time frames; at least annually.
- After all 8-day post second study vaccination safety data are available for all study participants.
- Final review meeting: 6 to 8 months after clinical database lock to review the cumulative unblinded safety and immunogenicity data for this trial. The data will be provided in a standard summary format. The DSMB may be asked to provide recommendations in response to questions posed by DMID.
- Ad hoc when a halting rule is met, for immediate concerns regarding observations during this trial, or as needed.

The DSMB will operate under the rules of a DMID-approved charter that will be written at the organizational meeting of the DSMB. At this time, each data element that the DSMB needs to assess will be clearly defined. Procedures for DSMB reviews/meetings will be defined in the charter. The DSMB will review applicable data to include, but not limited to, study progress and participant, clinical, safety, and reactogenicity data. Reports may include enrollment and demographic information, medical history, concomitant medications, physical assessments, clinical laboratory values, dosing compliance, and solicited and unsolicited AE/SAEs. Additional data may be requested by the DSMB, and interim statistical reports may be generated as deemed necessary and appropriate by DMID. The DSMB may receive data in aggregate and presented by treatment arm. The DSMB may also be provided with expected and observed rates of the expected AEs in an unblinded fashion, and may request the treatment arm be unblinded for an individual subject if required for safety assessment. The DSMB will review grouped and unblinded data in the closed session only. The DSMB will meet and review this data at scheduled time points or ad hoc as needed during this trial as defined in the DSMB charter. As an outcome of each review/meeting, the DSMB will make a recommendation as to the advisability of proceeding with study vaccinations (as applicable), and to continue, modify, or terminate this trial.

Additionally, SDCC web reports using data entered into AdvantageEDC will be monitored to determine if any of the halting rules described in [Section 9.5](#) are met.

If any of the halting rules are met, the study will not proceed with the remaining enrollment or study injections without a review by and recommendation from the DSMB to proceed.

Upon completion of this review and receipt of the advice of the DSMB, DMID will determine if study entry or study dosing should be interrupted or if study entry and study dosing may continue according to the protocol.

